4. STUDY DESIGN

4.1. GENERAL DESCRIPTION

This study is a multi-center, non-comparative, open-label, long-term extension study of migalastat HCl in subjects with Fabry disease who have completed treatment in a previous trial of migalastat HCl given as monotherapy. All subjects who were eligible for enrollment and completed migalastat HCl monotherapy treatment in a previous study, and who in the opinion of the investigator could benefit from remaining on migalastat HCl treatment were given the option to enroll into this trial. An alternative dosing regimen will be established per the addendum 1.1.2 for those

Document: \\quintiles.net\enterprise\Sites\CAMTL\IntProjects\SasData\Amicus\AT1001\AXA23225A\Biostatistics\Documentation\SAP\DR\Amicus_AT1001-042_SAP_Final_v1.0_20190821.docx

Author: Amicus

Version Number: Final v1.0

Version Date: 21AUG2019

Template No.: CS_TP_BS016 Revision 5

Reference: CS_WI_BS005

Effective Date: 01Apr2018

subjects with renal impairment (glomerular filtration rate (eGFR) < 30 mL/min/1.73m²), confirmed during the enrollment of the original protocol and amendment 1 and 1.1. The number of subjects to be enrolled in this study is expected to be up to 100, but is dependent on the number of eligible subjects completing migalastat HCl treatment in previous studies and who consent to enter this open-label extension study. Therefore, no sample size will be calculated.

The study will consist of a Baseline Visit (Visit 1) which will be performed at the time of the final visit of the previous study, followed by clinic visits every 6 months during the study. For the Addendum 1.1.2 subjects with renal impairment, clinical visits are performed approximately every 3 months. The duration of the treatment will vary among subjects and will continue until the date of regulatory approval or marketing authorization and/or commercialization in the participating subject's country, or study termination by the Sponsor, Amicus Therapeutics (Amicus).

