7.6. COMMON CALCULATIONS

For quantitative measurements, change from baseline will be calculated as:

- Change from Baseline = Test value at Visit X – Baseline Value
- Continuous variables (e.g., age) are summarized using descriptive statistics (the number of subjects with available data, mean, standard deviation [SD], median, minimum, and maximum). Categorical variables (e.g., gender) are summarized using counts and percentages. Percentages are calculated using the total subjects (per population).
- For continuous variables, all mean and median values are formatted to one more decimal place than the measured value. SD values are formatted to two more decimal places than the measured value. The minimum and maximum values are presented with the same number of decimal places as the measured value.
- For categorical variables, the number and percentage of responses are presented in the form XX (XX.X%) where the percentage is in the parentheses. In case of 0 counts, only “0” with no percentage will be presented and a percentage of 100 will not include decimals, e.g. 85 (100%).

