15. STUDY MEDICATION EXPOSURE AND ACCOUNTABILITY

Migalastat HCl, 150 mg per capsule, and reminder capsules in blister packs will be administered at the baseline visit and subsequent visits in 6-month intervals. Subjects are expected to take one 150 mg capsule every other day (QOD)

Document: \\quintiles.net\enterprise\Sites\CAMTL\IntProjects\SasData\Amicus\AT1001\AXA23225A\Biostatistics\Documentation\SAP\DR\Amicus_AT1001-042_SAP_Final_v1.0_20190821.docx

Author: Amicus

Version Number: Final v1.0

Version Date: 21AUG2019

Template No.: CS_TP_BS016 Revision 5

Reference: CS_WI_BS005

Effective Date: 01Apr2018

except for the Addendum 1.1.2 subjects, who are expected to take one 150 mg capsule on every 4th (Q4D) or 7th day (Q7D)..

Exposure to study medication will be presented for the ITT population by descriptive statistics. The date of first and last study medication administration will be taken from the eCRF Study Drug Administration form for duration of exposure as follows, and interruptions, compliance, and dose changes are not taken into account for duration of exposure.

Duration of exposure (days) = date of last study medication administration – date of first study medication administration + 1.

Duration of exposure (months) = Duration of exposure (days) / (365.25/12) rounded to one decimal place.

Duration of exposure [months] categorized by 6-month interval up to 48 months will also be included in the table. Listings presenting the study drug administration information including duration of exposure and drug accountability will be provided. In addition, a listing is provided to present dosing regimen for Addendum 1.1.2.

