18.1. ADVERSE EVENTS

Adverse Events (AEs) will be coded using Medical Dictionary for Regulatory Activities (MedDRA) central coding dictionary, Version 16.1 and will be summarized. The AE will be presented in summary tables for each of the following items, by the counts and percentages of subjects and events:

- The counts and percentages of subjects and events with each adverse event by SOC and preferred term
- The counts and percentages of subjects and events with each (investigator determined) treatment related adverse event by SOC and preferred term
- The counts and percentages of subjects and events with each adverse event leading to discontinuation of study medication by SOC and preferred term
- The counts and percentage of subjects and events with each serious adverse event by SOC and preferred term
- The counts and percentage of subjects and events with each adverse event leading to death
- Possible Suicidality Related Adverse Event (PSRAE)

Adverse events will also be summarized by the following categories:

- Severity
- Relationship to Study Drug

An overall summary of number of subjects and the events within each of the categories described in the sub-section

Document: \\quintiles.net\enterprise\Sites\CAMTL\IntProjects\SasData\Amicus\AT1001\AXA23225A\Biostatistics\Documentation\SAP\DR\Amicus_AT1001-042_SAP_Final_v1.0_20190821.docx

Author: Amicus

Version Number: Final v1.0

Version Date: 21AUG2019

Template No.: CS_TP_BS016 Revision 5

Reference: CS_WI_BS005

Effective Date: 01Apr2018

below, will be provided as specified in the templates.

A listing including all AEs will be provided. Separate listings for AEs Leading to Discontinuation of Study Medication, Serious AEs, AEs Leading to Death, and PSRAE will also be provided.

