18.1.1. ALL AEs

Incidence of AEs will be presented by System Organ Class (SOC) and Preferred Term (PT) and also broken down further by maximum severity and relationship to study medication. The following summary tables will be provided using counts and percentages of subjects and events:

- Overall summary of AEs
- Summary of AEs by SOC and PT
- Summary of AEs by PT
- Summary of AEs by SOC, PT and Severity
- Summary of AEs by SOC, PT and Relationship
- Summary of Serious AEs (SAE) by SOC and PT
- Summary of Non-serious AEs by SOC and PT
- Summary of Non-serious AEs by PT
- Summary of Non-serious AEs occurred in 5% or more of Subjects by SOC and PT
- Summary of AEs occurred in 5% or more of Subjects by SOC and PT

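### The SAP text gives adverse events no person-time denominator and no split by time on study, although treatment length is open-ended and varies by subject

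*SAP*

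**What the plan says.** SAP 18.1 lists its AE summaries by system organ class and preferred term, beginning with "The counts and percentages of subjects and events with each adverse event by SOC and preferred term". SAP 18.1.1 names ten tables under the same metric: "The following summary tables will be provided using counts and percentages of subjects and events". Two of the ten keep only AEs reached by at least 5% of subjects. The general rule in SAP 7.6 is "Percentages are calculated using the total subjects (per population".

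Treatment length is not fixed. SAP 4.1 states: "The duration of the treatment will vary among subjects and will continue until the date of regulatory approval", with marketing authorization, commercialization in the subject's country and sponsor termination as the other end points. Protocol 5.1 is equally open-ended. SAP 15 derives exposure for each subject as "Duration of exposure (days) = date of last study medication administration – date of first study medication administration + 1" and adds: "Duration of exposure [months] categorized by 6-month interval up to 48 months will also be included in the table". It does not connect that exposure to the AE tables.

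The one time split for AEs is in protocol 10.3.4.1 (treatment phase, follow-up phase and both combined). It does not adjust for differing treatment length, and SAP 18.1 does not carry it over.

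**The concern.** When subjects are observed for different lengths of time, the percentage with at least one event reflects both the risk per unit time and how long people were watched. A subject with 6 months in the study and one with 4 years count equally in the denominator. Follow-up here depends partly on when each country reaches approval or commercialization and partly on withdrawal under protocol 6.4 and 8.2.2, so it need not be similar across subjects.

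The primary objective is long-term safety. Two natural questions are whether event rates differ from those in the feeder studies and whether they change with continued treatment. Protocol 3.2 gives the two pivotal studies lengths of 24 and 18 months, so a percentage from an open-ended extension is not on the same time base. Without a split by time on study, no planned table addresses the second question. The SAP already accepts the principle for efficacy: SAP 17.1.1 and 17.1.2 annualize the eGFR change.

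**Working it through.** The plan states no AE rate and no sample-size calculation (protocol 10.2), so there is no figure of its own to reproduce. The check asks how far the planned statistic moves when only follow-up changes.

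**Inputs**
- Follow-up t: 0.5 to 4 years, the span of the 6-month to 48-month bands in SAP 15. This is a table layout, not an observed distribution.
- First-event rate λ: not in the documents. Assumed constant over time, and shown at 2, 5, 10 and 100 per 100 patient-years.

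**Step 1: crude percentage when every subject has follow-up t.** Formula: 100 × (1 − exp(−λt)).

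| First events per 100 patient-years | 6 months | 12 months | 24 months | 48 months | Ratio, 48 to 6 months |
|---|---|---|---|---|---|
| 2 | 1.0% | 2.0% | 3.9% | 7.7% | 7.7 |
| 5 | 2.5% | 4.9% | 9.5% | 18.1% | 7.3 |
| 10 | 4.9% | 9.5% | 18.1% | 33.0% | 6.8 |
| 100 | 39.3% | 63.2% | 86.5% | 98.2% | 2.5 |

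Ratios use unrounded values; for example, at 10 per 100, 0.3297 / 0.0488 = 6.76. For uncommon events the percentage is close to rate × time, so the ratio approaches the 8-fold ratio of times. For very common events it saturates and the dependence weakens.

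**Step 2: the reverse reading.** Formula: λ = −ln(1 − p) / t. A reported 10% corresponds to 21.1 per 100 patient-years if all subjects had 6 months, 10.5 at 1 year, 5.3 at 2 years and 2.6 at 4 years.

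**Step 3: the 5% tables.** −ln(0.95) = 0.0513. Reaching 5% needs 0.0513 / 0.5 = 10.3 per 100 patient-years at 6 months, but 0.0513 / 4 = 1.3 at 48 months. Which terms enter those tables therefore depends on follow-up.

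**Step 4: one pooled cohort, as the SAP would report it.** Take 100 subjects at 10 per 100 patient-years, half followed 0.5 years and half 4 years. Patient-years are 50 × 0.5 + 50 × 4 = 225. The crude percentage is (4.9 + 33.0) / 2 = 18.9% (unrounded inputs), compared with 9.5% if all had 1 year and 33.0% if all had 4. If events can recur at the same rate, the expected count is 22.5, and 22.5 / 225 returns 10 per 100 patient-years, the rate put in.

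**Step 5: can the Section 15 duration serve as the denominator?** It stops at the last dose. Protocol 8.2.10 collects AEs until the earlier of the follow-up contact and 30 days after the last dose. The uncounted window is at most 30 / 182.6 = 16% of a 6-month exposure and 30 / 1461 = 2% of a 48-month exposure. The mismatch therefore weighs most on short-stay subjects. Nor does Section 15 give time to first onset, which a first-event rate needs.

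**The case against.** The strongest reply is that this is a non-comparative, descriptive study with no hypothesis test (protocol 10.1, SAP 7.5). The protocol itself asks for percentages of subjects, and no AE comparison with the feeder studies is planned. Event counts are shown beside the percentages, exposure is summarized, and listings give AEs with study day. A reader could divide the event count by number of subjects × mean exposure. The information exists; only a column is missing.

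Much of that stands. A reader might infer that AEs appear only as crude percentages; they do not, because subject and event counts are planned too. A reader might also infer a bias in a treatment comparison; there is no second arm, so there is none. The 48-month bands might be read as showing that follow-up spans eight bands or several years, but they are a table layout, and the text says only that duration varies. The ratios in Step 1 might be taken as the error in a planned table; they contrast hypothetical cohorts at assumed rates, whereas the SAP reports one pooled figure.

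What does not stand is the conclusion that nothing is lost. The back-calculation gives only a rough overall event rate. It supplies no first-event rate and no view of risk over time. A rate per 100 patient-years is itself descriptive, so the absence of testing is no reason to omit it. SAP 18.1 refers the overall AE summary to templates that were not available, so a rate column there cannot be excluded; if one exists, the SAP text should say so.

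**Conclusion.** The point holds as a limit on interpretation. In the SAP text supplied, no AE summary has a person-time denominator or a split by time on study, while treatment length is open-ended. The percentages and the 5% cut-off therefore combine risk with length of follow-up, which matters because long-term safety is the primary objective.

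The size depends on event frequency: between follow-up of 6 and 48 months for everyone, 7.7-fold at 2, 6.8-fold at 10 and 2.5-fold at 100 first events per 100 patient-years. These figures rest on a constant hazard, assumed rates and the SAP's band limits as the span of follow-up. The actual effect depends on the mix of durations, which the documents do not give. The documents do not support calling the planned percentages erroneous: they are valid descriptions of the cohort, but cannot be read as risk per unit time.

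**What to change.** In SAP 18.1 and 18.1.1, keep the crude counts and percentages and make these additions:

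- **Rates.** In the overall, serious, treatment-related and discontinuation tables, add subjects with a first event per 100 patient-years and events per 100 patient-years.
- **Time on study.** Add one table of AE incidence by year on this study, with the subjects at risk in each interval as denominator. A single overall rate cannot show whether risk changes.
- **Time at risk.** Run it from first dose in this study to the end of the AE collection window in protocol 8.2.10, not over the first-to-last-dose duration of SAP 15. Censor it at first onset for the first-event rate.
- **Partial onset dates.** State a rule. SAP 7.1 leaves study day partial or missing and SAP 8.3 allows no imputation, so such events could not otherwise be placed in an interval.
- **Footnote.** Say that year on study is not total time on migalastat, because subjects enter already treated (SAP 7.2).

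The cost is modest extra programming, a few columns and one interval table. No new data collection is needed.

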18.1.1. ALL AEs

Incidence of AEs will be presented by System Organ Class (SOC) and Preferred Term (PT) and also broken down further by maximum severity and relationship to study medication. The following summary tables will be provided using counts and percentages of subjects and events:

- Overall summary of AEs
- Summary of AEs by SOC and PT
- Summary of AEs by PT
- Summary of AEs by SOC, PT and Severity
- Summary of AEs by SOC, PT and Relationship
- Summary of Serious AEs (SAE) by SOC and PT
- Summary of Non-serious AEs by SOC and PT
- Summary of Non-serious AEs by PT
- Summary of Non-serious AEs occurred in 5% or more of Subjects by SOC and PT
- Summary of AEs occurred in 5% or more of Subjects by SOC and PT

18.1.1.1. Severity

Severity is classified as mild/ moderate/ severe (increasing severity). AEs with a missing severity will be classified as severe. If a subject reports an AE more than once within that SOC/ PT, the AE with the worst-case severity will be used in the corresponding severity summaries.

18.1.1.2. Relationship to Study Medication

Relationship, as indicated by the Investigator, is classified as “Unrelated”, “Unlikely”, “Possible”, “Probable”, and “Definite” (increasing level of relationship). A “Potentially Related” AE is defined as an AE with a relationship to study medication as “Possible”, “Probable” or “Definite” to study medication. AEs with a missing relationship to study medication will be regarded as “Potentially related” to study medication. If a subject reports the same AE more than once within that SOC/PT, the AE with the worst-case relationship to study medication will be used in the corresponding relationship summaries.

Document: \\quintiles.net\enterprise\Sites\CAMTL\IntProjects\SasData\Amicus\AT1001\AXA23225A\Biostatistics\Documentation\SAP\DR\Amicus_AT1001-042_SAP_Final_v1.0_20190821.docx

Author: Amicus

Version Number: Final v1.0

Version Date: 21AUG2019

Template No.: CS_TP_BS016 Revision 5

Reference: CS_WI_BS005

Effective Date: 01Apr2018

18.1.2. AEs LEADING TO DISCONTINUATION OF STUDY MEDICATION

AEs leading to permanent discontinuation of study medication will be identified by using the eCRF AE form with “Stopped Permanently” recorded for question “Action Taken with Study Drug”. For AEs leading to discontinuation of study medication, a summary on the number of subjects and events by SOC and PT will be prepared.

18.1.3. SERIOUS ADVERSE EVENTS

Serious adverse events (SAEs) are those events recorded as “Yes” to the question “Serious” on the Adverse Events page of the eCRF. A summary of serious AEs on the number of subjects and events by SOC and PT will be prepared.

18.1.4. NON-SERIOUS ADVERSE EVENTS

A summary of non-serious AEs (excluding SAEs) by SOC and PT will be prepared. A supporting listing will also be provided for non-serious AEs.

18.1.5. ADVERSE EVENTS LEADING TO DEATH

AEs leading to Death are those events which are recorded as having “Fatal Outcomes” on the Adverse Events page of the eCRF.

18.1.6. POSSIBLE SUICIDALITY RELATED ADVERSE EVENT (PSRAE)

If an occurrence of an adverse event which, in the investigator’s opinion, is possibly related to suicidality, it will be recorded on the PSRAE eCRF form and reported under this category. The AE number of PSRAE will be collected in the PSRAE eCRF, which will be linked to the particular AEs in the AE eCRF pages in EDC. A summary of PSRAE by SOC and PT will be prepared.

A listing with SOC and PT for PSRAE will be presented. In addition, all other information captured in the PSRAE eCRF will be presented in another listing.

18.2. PHYSICAL EXAMS

A data listing will be provided to present physical examination findings.

Document: \\quintiles.net\enterprise\Sites\CAMTL\IntProjects\SasData\Amicus\AT1001\AXA23225A\Biostatistics\Documentation\SAP\DR\Amicus_AT1001-042_SAP_Final_v1.0_20190821.docx

Author: Amicus

Version Number: Final v1.0

Version Date: 21AUG2019

Template No.: CS_TP_BS016 Revision 5

Reference: CS_WI_BS005

Effective Date: 01Apr2018

18.3. VITAL SIGNS

Vital Signs will be assessed at each study visit and results will be summarized descriptively by study visit for baseline, post-baseline visit and change from baseline.

The following Vital Signs measurements will be reported for this study:

- Sitting / Supine Systolic Blood Pressure (mmHg)
- Sitting / Supine Diastolic Blood Pressure (mmHg)
- Heart Rate (bpm)
- Respiratory Rate (breaths/min)
- Temperature (^oC)
- Weight (kg)
- Height (cm)
- BMI (kg/m²)

Body Mass Index (BMI) will be calculated using the same formula as baseline: BMI (kg/m²) = weight (kg)/ height (m)² of the same visit. It will be reported only for Baseline and Study Completion Visits.

Each measurement of the following parameters will be evaluated against the criteria of abnormality detailed below for potentially clinically significant vital signs. Potentially clinically significant vital signs are derived and categorized into PCS Low and PCS High, as well as Normal. In addition, a table summarizing the counts and percentages of each PCS category at any time including unscheduled visits will be presented.

Vital Signs	Criteria	Abnormality Categories
Pulse	≥ 120 bpm at any post-baseline time point and ≥ 15 bpm increase from baseline at any post-baseline time point	PCS High
	≤ 50 bpm at any post-baseline time point and ≥ 15 bpm decrease from baseline at any post-baseline time point	PCS Low
Systolic blood pressure	≥ 180 mm Hg at any post-baseline time point and ≥ 20 mm Hg increase from baseline at any post-baseline time point	PCS High
	≤ 90 mm Hg at any post-baseline time point and ≥ 20	PCS Low

Document: \\quintiles.net\enterprise\Sites\CAMTL\IntProjects\SasData\Amicus\AT1001\AXA23225A\Biostatistics\Documentation\SAP\DR\Amicus_AT1001-042_SAP_Final_v1.0_20190821.docx

Author: **Amicus** Version Number: **Final v1.0**
 Version Date: **21AUG2019**

Template No.: CS_TP_BS016 Revision 5 Reference: CS_WI_BS005

Effective Date: 01Apr2018

Vital Signs	Criteria	Abnormality Categories
	mm Hg decrease from baseline at any post-baseline time point	
Diastolic blood pressure	≥ 105 mm Hg at any post-baseline time point and ≥ 15 mm Hg increase from baseline at any post-baseline time point	PCS High
	< 40 mm Hg at any post-baseline time point and ≥ 15 mm Hg decrease from baseline at any post-baseline time point	PCS Low
Weight	≥ 7% change from baseline at any post-baseline time point	PCS High

A listing presenting all available vital signs assessments for subjects with potentially clinically significant vital signs any time during the study will be provided.

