18.6. ECHOCARDIOGRAPHY (ECHO)

ECHO parameters are categorized into Normal, Mildly Abnormal, Moderately Abnormal, Severely Abnormal (or Low, Normal, High) by gender (or age) based on the criteria below for safety purpose, and a table presenting counts and percentages of each category by parameter and visit will be provided. A table presenting Severely Abnormal incidence at any visits through the study including unscheduled visits will be included.

ECHO Parameters	Criteria for Female	Criteria for Male	Abnormality Category
Left Ventricular Posterior Wall Thickness Diastole (cm) (LVPWTD)	0.6 - 0.9	0.6 - 1.0	Normal
	1.0 - 1.2	1.1 - 1.3	Mildly Abnormal

Document: \\quintiles.net\enterprise\Sites\CAMTL\IntProjects\SasData\Amicus\AT1001\AXA23225A\Biostatistics\Documentation\SAP\DR\Amicus_AT1001-042_SAP_Final_v1.0_20190821.docx

Author: Amicus

Version Number: Final v1.0

Version Date: 21AUG2019

Template No.: CS_TP_BS016 Revision 5

Reference: CS_WI_BS005

Effective Date: 01Apr2018

ECHO Parameters	Criteria for Female	Criteria for Male	Abnormality Category
	1.3 - 1.5	1.4 - 1.6	Moderately Abnormal
	≥ 1.6	≥ 1.7	Severely Abnormal
Intraventricular Septum Thickness Diastolic (cm) (IVSTD)	0.6 - 0.9	0.6 - 1.0	Normal
	1.0 - 1.2	1.1 - 1.3	Mildly Abnormal
	1.3 - 1.5	1.4 - 1.6	Moderately Abnormal
	≥ 1.6	≥ 1.7	Severely Abnormal
Left Ventricular Ejection Fraction (%) (LVEF)	≥ 55	Same as female	Normal
	45 - 54	Same as female	Mildly Abnormal
	30 - 44	Same as female	Moderately Abnormal
	< 30	Same as female	Severely Abnormal
Fractional Shortening (%) (FS)	27 - 45	25 - 43	Normal
	22 - 26	20 - 24	Mildly Abnormal
	17 - 21	15 - 19	Moderately Abnormal
	≤ 16	≤ 14	Severely Abnormal
Left Ventricular Mass (g) (LVM)	67 - 162	88 - 224	Normal
	163 - 186	225 - 258	Mildly Abnormal
	187 - 210	259 - 292	Moderately Abnormal
	≥ 211	≥ 293	Severely Abnormal
Left Ventricular Mass Index (g/m ²) (LVMI)	43 - 95	49 - 115	Normal

Document: \\quintiles.net\enterprise\Sites\CAMTL\IntProjects\SasData\Amicus\AT1001\AXA23225A\Biostatistics\Documentation\SAP\DR\Amicus_AT1001-042_SAP_Final_v1.0_20190821.docx

Author: Amicus

Version Number: Final v1.0

Version Date: 21AUG2019

Template No.: CS_TP_BS016 Revision 5

Reference: CS_WI_BS005

Effective Date: 01Apr2018

ECHO Parameters	Criteria for Female	Criteria for Male	Abnormality Category
	96 - 108	116 - 131	Mildly Abnormal
	109 - 121	132 - 148	Moderately Abnormal
	≥ 122	≥ 149	Severely Abnormal

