Peak Mitral Inflow Velocity E (cm/s) (EPOINT)	For age < 50	Same as female	
	< 58	Same as female	Low
	58 - 86	Same as female	Normal
	> 86	Same as female	High
	For age ≥ 50	Same as female	
	< 48	Same as female	Low
	48 - 76	Same as female	Normal
	> 76	Same as female	High
Peak Mitral Inflow Velocity A (cm/s) (APOINT)	For age < 50	Same as female	
	< 30	Same as female	Low
	30 - 50	Same as female	Normal
	> 50	Same as female	High
	For age ≥ 50	Same as female	
	< 45	Same as female	Low
	45 - 73	Same as female	Normal
	> 73	Same as female	High

Document: \\quintiles.net\enterprise\Sites\CAMTL\IntProjects\SasData\Amicus\AT1001\AXA23225A\Biostatistics\Documentation\SAP\DR\Amicus_AT1001-042_SAP_Final_v1.0_20190821.docx

Author: Amicus

Version Number: Final v1.0

Version Date: 21AUG2019

Template No.: CS_TP_BS016 Revision 5

Reference: CS_WI_BS005

Effective Date: 01Apr2018

ECHO Parameters	Criteria for Female	Criteria for Male	Abnormality Category
Mitral Valve E/A Ratio (EARATIO)	For age < 50	Same as female	
	< 1.3	Same as female	Low
	1.3 - 2.5	Same as female	Normal
	> 2.5	Same as female	High
	For age >= 50	Same as female	
	< 0.8	Same as female	Low
	0.8 - 1.4	Same as female	Normal
	> 1.4	Same as female	High
Left Ventricular Internal Dimension at End Diastole (cm) (LVIDd)	3.5 - 5.3	4.2 - 5.9	Normal
	5.4 - 5.7	6.0 - 6.3	Mildly Abnormal
	5.8 - 6.1	6.4 - 6.8	Moderately Abnormal
	>= 6.2	>= 6.9	Severely Abnormal
Left Ventricular Internal Dimension at End Systole (cm) (LVIDs)	2.49 - 3.15	2.87 - 3.61	Normal
Midwall Fractional Shortening (%) (MWFS)	15 - 23	14 - 22	Normal
	13 - 14	12 - 13	Mildly Abnormal
	11 - 12	11	Moderately Abnormal
	<= 10	<= 10	Severely Abnormal

Systolic and diastolic function grading with respect to the abnormality categories are available in the data and will

Document: \\quintiles.net\enterprise\Sites\CAMTL\IntProjects\SasData\Amicus\AT1001\AXA23225A\Biostatistics\Documentation\SAP\DR\Amicus_AT1001-042_SAP_Final_v1.0_20190821.docx

Author: Amicus

Version Number: Final v1.0

Version Date: 21AUG2019

Template No.: CS_TP_BS016 Revision 5

Reference: CS_WI_BS005

Effective Date: 01Apr2018

be presented in the same table as parameters listed above.

ECHO comments and other information (parameters other than those listed above) will be presented in two other listings.

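### The weight criterion in SAP 18.3 has no direction, so a loss of 7% or more can never be PCS Low; as a lesser point, LVIDs in SAP 18.6 has a Normal band and no abnormal category

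*SAP*

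**What the plan says.** **Weight.** SAP 18.3 says that potentially clinically significant vital signs are "categorized into PCS Low and PCS High, as well as Normal". The criteria table covers pulse, systolic pressure, diastolic pressure and weight. Each of the first three has a High row worded as an increase and a Low row worded as a decrease. Weight has a single row, "≥ 7% change from baseline at any post-baseline time point", with the label PCS High.

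The categories feed a count table that includes unscheduled visits, and a listing: "A listing presenting all available vital signs assessments for subjects with potentially clinically significant vital signs any time during the study will be provided".

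The only definition of change is in SAP 7.6: "Change from Baseline = Test value at Visit X – Baseline Value". That is a signed difference in units. Percent change is not defined.

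**LVIDs.** SAP 18.6 states: "ECHO parameters are categorized into Normal, Mildly Abnormal, Moderately Abnormal, Severely Abnormal (or Low, Normal, High) by gender (or age". For the row "Left Ventricular Internal Dimension at End Systole (cm) (LVIDs" the table gives a Normal band only: 2.49 to 3.15 cm for females and 2.87 to 3.61 cm for males. LVIDd has all four grades. The mitral inflow parameters, starting with "Peak Mitral Inflow Velocity E (cm/s) (EPOINT", and the E/A ratio have Low, Normal and High written out.

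**The concern.** Safety is the primary objective, and the PCS table is where a reader would look for the number of subjects with marked weight loss. The row as written cannot give that number. Two programmers could also produce different tables from the same data, because the text does not settle whether the change is signed or absolute.

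The PCS table matters more for off-schedule data. SAP 7.3 and SAP 18 keep unscheduled measurements out of the by-visit summaries. A loss seen only at an unscheduled visit is therefore summarised only through this row and otherwise appears only in listings.

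For LVIDs, a value outside the Normal band has no assigned place in the echo category table, in either of the two schemes that the SAP names.

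**Working it through.** The plan gives no figure to reproduce. The check applies the printed rules to test values.

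**Weight inputs.** The threshold is 7% and the label is PCS High (SAP 18.3). The baseline of 70.0 kg is an assumption; the category depends only on the percent change.

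Formula: percent change = 100 × (visit − baseline) / baseline.

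- Loss: 100 × (65.1 − 70.0) / 70.0 = −7.0%
- Gain: 100 × (74.9 − 70.0) / 70.0 = +7.0%

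| Percent change | Weight (kg) | Absolute reading | Signed reading | Split row |
|---|---|---|---|---|
| −15 | 59.5 | PCS High | Normal | PCS Low |
| −7 | 65.1 | PCS High | Normal | PCS Low |
| −6.9 | 65.17 | Normal | Normal | Normal |
| +6.9 | 74.83 | Normal | Normal | Normal |
| +7 | 74.9 | PCS High | PCS High | PCS High |
| +15 | 80.5 | PCS High | PCS High | PCS High |

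To show how counts would differ, suppose that five subjects lose 7% and three gain 7%, with no other flagged vital sign. These numbers are hypothetical and say nothing about how often this occurs.

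- Absolute reading: High 5 + 3 = 8, Low 0, Normal 0; all 8 are in the PCS listing.
- Signed reading: High 3, Low 0, Normal 5; 3 of the 8 are in the PCS listing.
- Split row: High 3, Low 5, Normal 0; all 8 are in the listing.

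**LVIDs inputs.** The Normal limits are those printed in SAP 18.6.

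| Sex | Value (cm) | As printed | With Low and High added |
|---|---|---|---|
| Female | 2.48 | no category | Low |
| Female | 2.49 to 3.15 | Normal | Normal |
| Female | 3.16 | no category | High |
| Male | 2.86 | no category | Low |
| Male | 2.87 to 3.61 | Normal | Normal |
| Male | 3.62 | no category | High |

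The table has 12 echo parameters: LVPWTD, IVSTD, LVEF, FS, LVM, LVMi, E, A, E/A, LVIDd, LVIDs and MWFS. Eleven have at least one category other than Normal, and LVIDs has none.

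**The case against.** **Weight losses may well be captured.** The other three vital signs name a direction in every row, and weight alone speaks of change. That contrast favours a two-sided criterion, and SAP 7.6 does not rebut it because it defines a difference in units. On that reading a 7% loss is counted, the subject is listed, and the listed weights show the direction. This stands. A reader might infer that weight loss goes unflagged in this trial; the documents do not support that as the likely outcome. What remains is that losses carry the label for a high value and share a count with gains.

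**Little else depends on it.** Protocol 10.3.4.1 asks only for by-visit summaries of vital signs and weight with changes from baseline, and the SAP provides them. Protocol 8.2.5 has clinically significant worsening recorded as an adverse event, with an exception for findings tied to the underlying disease and no more severe than expected. This stands too, and it limits the point to minor.

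**A programmer could treat LVIDs as Low, Normal, High.** This is possible, since the SAP names that scheme. But it does not assign the scheme to LVIDs, and it writes out the Low and High rows where it does use it.

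**Stronger echo readings.** A reader might infer that an LVIDs value outside Normal and a missing echo would look alike in the table, because SAP 7.6 says "Percentages are calculated using the total subjects (per population". That depends on whether the table has a count, missing or other row. SAP 9 places format and content in templates that were not available, so the inference is not established. A reader might also see gaps between bands, or on the ungraded side of Normal, for other echo parameters. Whether values fall between bands depends on recording precision and rounding, which the SAP does not state; at printed precision none do. For the ungraded side, those parameters at least have abnormal grades. Neither is part of this point.

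**Rows lost in text extraction.** This cannot be fully excluded, but neither table shows a gap or redaction at these rows.

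**Conclusion.** The point holds on the text and is minor. As written, no weight loss of any size can be PCS Low. Losses of 7% or more are PCS High mixed with gains on the more natural reading, or Normal on the signed reading. Only on the signed reading does a subject whose sole event is weight loss drop out of the PCS listing.

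The LVIDs gap is real but smaller: one parameter of 12 has no category outside Normal, and SAP 17.1.6 still summarises it by visit with change from baseline.

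The effect is confined to descriptive category counts and one listing. No test or protocol-required summary is affected, and the values remain in the general listings. The conclusion assumes that the templates do not already contain the missing rules.

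**What to change.** - **Weight:** replace the single row with two at the existing threshold: an increase of at least 7% is PCS High, and a decrease of at least 7% is PCS Low. Add to SAP 7.6: percent change = 100 × (visit − baseline) / baseline.
- **LVIDs:** label values below the existing Normal limits Low and values above them High, in the form already used for E, A and E/A. Alternatively, state that LVIDs is not categorised. The documents contain no cut-offs for severity grades, so LVIDs would still not enter the Severely Abnormal table; say so.
- If the templates already hold these rules, refer to them from the two SAP tables.

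The cost is a few table rows, one definition and small programming changes. No new data are needed.
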